2.2 TRIAL OBJECTIVES

The primary objective of this trial is to investigate the safety and tolerability of single rising doses of BI 473494 administered subcutaneously in healthy male subjects.

The secondary objective is the exploration of PK including dose proportionality, of BI 473494 after single dosing.

A description of the endpoints to be determined, and the observations along with specific information as how to collect the data for that information, is provided in [Section 5](#).

2.3 BENEFIT - RISK ASSESSMENT

Participation in this study is without any (therapeutic) benefit for healthy subjects. Their participation in the study, however, is of major importance to the development of a new long-acting subcutaneous drug which might improve therapy for obesity with or without T2D. The subjects are exposed to the risks of the study procedures and the risks related to the exposure to the trial medication.

Procedure-related risks

The use of an indwelling venous catheter for the purpose of blood sampling may be accompanied by mild bruising and also, in rare cases, by transient inflammation of the wall of the vein. In addition, in rare cases a nerve might be injured while inserting the venous catheter, potentially resulting in paraesthesia, reduced sensibility, and/or pain for an indefinite period. The same risks apply to veinpuncture for blood sampling.

The total volume of blood withdrawn during the entire study per subject will not exceed the volume of a normal blood donation (500 mL). No health-related risk to healthy subjects is expected from this blood withdrawal.

Drug-related risks and safety measures

Since the nature of the target and the mode of action of BI 473494 are well understood - a short-acting compound from the same class (amylin agonist) has been marketed for over a decade - and the animal models used are believed to be predictive for the effects in humans, BI 473494 is not seen as a high risk compound. The pharmacological effects of BI 473494 are dose-dependent and no evidence for prolonged effects or effects other than those expected by the pharmacological activity of the compound have been observed. Following repetitive dosing, plasma exposures

are supported by preclinical safety data in Cynomolgus monkey and rats, respectively.

To ascertain the safety and minimize the risk for healthy volunteers, several safety measures and investigations will be implemented in this trial:

- Only healthy volunteers will be included according to the in- and exclusion criteria.
- Careful dose selection as described in [Section 2.1](#). The start dose is selected with due caution and has ample safety margins with respect to both, NOAEL in the most sensitive species and pharmacodynamic effects. Dose escalation will be shallow as outlined in [Section 2.1](#). Finally, dose selection was based on a sound preclinical package including 6 weeks toxicological studies.
- Preliminary measurement of BI 473494 plasma concentrations and preliminary determination of PK parameters (AUC, C_{max} , see [Section 7.3.4](#)). For the sake of caution, drug plasma concentrations of healthy male volunteers in this trial will be considered as a preliminary threshold (see [Section 2.1](#)). Further dose escalation beyond these thresholds would only be allowed after a safety interim analysis and filing and approval of a substantial CTP amendment.

Proprietary confidential information © 2017 Boehringer Ingelheim International GmbH or one or more of its affiliated companies

- An extensive safety laboratory will be performed with special focus on full blood exam (see time points in the [Flow Chart](#)).
- For safety reasons, each dose group of 8 subjects (6 on active, 2 on placebo) will be divided into 3 cohorts. The 1st and 2nd cohort will each comprise 2 subjects, the 3rd cohort will be a group of 4 subjects. Investigational drug administrations in these three cohorts will be separated by at least 72 hours (between 1st subject of each cohort), which is based on an anticipated median t_{max} of BI 473494 of 16-20 h (as derived from the median t_{max} of semaglutide in humans [[R17-0493](#)]) and median t_{max} of 32-40 h (as derived from the 6 weeks toxicology study in Cynomolgus monkeys [[n00253475](#)]) and is expected to cover the period of highest risk and peak pharmacodynamic effects. The first 2 cohorts will be dosed in a single blind, fixed sequence mode 'active – placebo' (1st cohort) and 'active – active' (2nd cohort). This design ensures that there is a time interval of at least 72 hours between first and second active dose of each dose level. This is expected to be sufficient to detect relevant acute effects of BI 473494. If BI 473494 was safe and well tolerated during the first administration, the remaining subjects of the respective dose level could be dosed as close as 10 minutes apart.
- A thorough ECG monitoring to cover the anticipated period of highest drug exposure with triple 12-lead ECGs over 29 Days following SC drug administration. Dose escalation would be stopped as soon as at least 2 subjects at one dose level showed relevant QT prolongation (see [Section 3.3.4.2](#) for details).
- Vital signs, body weight, aural body temperature will be assessed at time points given in the [Flow Chart](#).
- Although the risk of hypoglycaemic events is considered to be low for BI 473494 based on its mode of action

In summary, the information gained from this trial will provide the basis for further clinical development of the long-acting amylin analogue BI 473494 which is expected to become a valuable therapeutic option for patients with obesity and T2D. BI 473494 has a favourable benefit-risk-assessment which allows safe testing in humans. Based on a thorough preclinical data package as well as knowledge gained from more than 10 years of experience with the short-acting amylin analogue pramlintide, as well as the implemented safety measures described above, healthy subjects will not be exposed to unacceptable risk in relation to the important information expected from this trial. Healthy volunteers are not expected to have any direct benefit from participation in the first-in-human trial with BI 473494, as is usually the case in such phase I trials. Considering the medical need regarding the treatment of obesity and T2D, the Sponsor considers that the benefit outweighs the potential risks and justifies exposure of healthy human volunteers.

3. DESCRIPTION OF DESIGN AND TRIAL POPULATION

3.1 OVERALL TRIAL DESIGN AND PLAN

This single-rising dose trial is designed as single-blind, partially randomised, and placebo-controlled within parallel dose groups.

A total of 88 healthy male subjects is planned to participate in the trial, according to 11 sequential groups comprising 8 subjects per group. However, additional subjects may be entered to allow testing of additional doses on the basis of experience gained during the trial conduct (e.g. preliminary PK data), provided the planned and approved highest dose will not be exceeded. Thus, the actual number of subjects entered may exceed 88, but will not exceed 104 subjects entered. Such changes may be implemented via non-substantial CTP amendment.

Within each dose group, 6 subjects will receive the active drug and 2 will receive placebo. Only one dose is tested within each dose group. Each dose group will consist of 3 cohorts which will be treated subsequently for safety reasons.

The dose groups to be evaluated are outlined in [Table 3.1: 1](#) below.

Table 3.1: 1 Dose groups

The dose groups will be investigated consecutively in ascending order of doses, maintaining a time interval of at least 7 days between the last drug administration in the previous dose group and the first drug administration of the subsequent dose group.

The decision to proceed to the next dose group will be based upon the safety, tolerability and on pharmacokinetic data of the preceding dose groups. The next dose will only be given if, in the opinion of the Investigator, no safety concerns arose in the preceding dose group (i.e. no dose-limiting events occurred) and if none of the pre-specified trial-specific stopping criteria were met (refer to [Section 3.3.4.2](#)).

A documented Safety Review must take place prior to each dose escalation. Furthermore, an unscheduled safety review meeting can be requested anytime for any reasonable cause by the Principal Investigator (or an authorised deputy) or the Sponsor of the study, e.g. because of

Proprietary confidential information © 2017 Boehringer Ingelheim International GmbH or one or more of its affiliated companies

any unforeseen adverse events, etc. Dose escalation will only be permitted if no safety concerns exist in the opinion of the Principal Investigator (or an authorised deputy) and the Trial Clinical Monitor (or an authorised deputy).

The minimum data set for review consists of the following data (for the current dose group safety data of at least 3 days following BI 473494 or placebo administration in at least 6 subjects should be considered):

- AEs in the current and preceding dose groups, including clinically relevant findings from ancillary safety testing listed below (note: AEs may be ongoing at the time of Safety Reviews and AE information may be subject to change prior to Database Lock)
- Results from 12-lead ECG in the current and preceding dose groups.
- Vital signs in the current and preceding dose groups
- Clinical laboratory tests in the current and preceding dose groups
-
- Preliminary PK data as per [Section 7.3.4](#).
- Check of criteria for stopping subject treatment as per [Section 3.3.4.1](#)

The decision to escalate the dose will be made jointly by the Principal Investigator (or an authorised deputy) and the Trial Clinical Monitor (or an authorised deputy) after in-depth analysis of all available safety data, especially SAEs (if occurred), AEs and out-of-range laboratory results (if considered clinically significant). Safety Reviews can be conducted face-to-face or by video/telephone conference. The Trial Clinical Monitor is responsible for organization and minutes of the reviews. Minutes will be signed off by the Principal Investigator (or an authorised deputy) and filed in the ISF and TMF.

The Investigator (after consultation with the Sponsor) is allowed to alter the scheduled dose levels (e.g. add low and/or intermediate dose levels) provided the planned and approved highest dose is not exceeded and to prolong in-house confinement on the basis of experience gained during the study. In the case of additional dose levels, the total number of subjects in this trial might increase. The Investigator and/or the Sponsor should stop dose escalation in case the safety evaluation leads to concerns that would not allow higher dosing.

An overview of all relevant trial activities is provided in the [Flow Chart](#). For visit schedules and details of trial procedures at selected visits, refer to [Sections 6.1](#) and [6.2](#), respectively.

3.1.1 Administrative structure of the trial

The trial is sponsored by Boehringer Ingelheim (BI) Pharma GmbH & Co. KG, Germany.

BI has appointed a Trial Clinical Monitor, responsible for coordinating all required activities, in order to

- manage the trial in accordance with applicable regulations and internal SOPs,
- direct the clinical trial team in the preparation, conduct, and reporting of the trial,
- ensure appropriate training and information of local clinical monitors (CML), Clinical Research Associates (CRAs), and participating trial sites.

Proprietary confidential information © 2017 Boehringer Ingelheim International GmbH or one or more of its affiliated companies

The BI investigational product BI 473494 will be provided by the Clinical Trial Supplies Unit (CTSU), BI Pharma GmbH & Co. KG, Biberach, Germany. The comparator product (isotonic sodium chloride solution, Braun, as placebo)

The trial will be conducted at
, under the supervision of the Principal Investigator.

Safety laboratory tests will be performed by the local laboratory of the trial site

The analyses of BI 473494 concentrations in plasma and urine will be performed at the Department of Drug Metabolism and Pharmacokinetics, BI Pharma GmbH & Co. KG, Biberach, Germany.

The digitally recorded 12-lead ECGs will be sent to a specialised contract research organisation () for evaluation.

On-site monitoring will be performed by BI or a contract research organisation appointed by BI.

Data management will be done by BI according to BI SOPs. Statistical tasks and programming will be performed by according to BI SOPs.

Tasks and functions assigned in order to organise, manage, and evaluate the trial are defined according to BI SOPs. A list of responsible persons and relevant local information can be found in the ISF.

3.2 DISCUSSION OF TRIAL DESIGN, INCLUDING THE CHOICE OF CONTROL GROUP

For single-rising dose trials, the design described in [Section 3.1](#) is viewed favourable under the provision not to expose the subjects involved to undue risks since the main study objective is to investigate safety and tolerability of BI 473494. To minimize risk for subjects, administration of ascending doses will be applied in a sequential manner with no overlap between dose groups for at least 7 Days after dosing of last cohort in each dose group. Moreover, the first four subjects in each dose group will be treated in fixed-sequence (1. Active, 2. Placebo, 3. Active, 4. Active). With the rising dose design, single-blind conditions regarding the subject's treatment (active or placebo) are maintained within each dose group. However, the current dose level will be known to subjects and investigators.

Proprietary confidential information © 2017 Boehringer Ingelheim International GmbH or one or more of its affiliated companies

The disadvantage of this trial design is a possible observer bias with regard to the dose-dependent effects as well as time effects, but it has the virtue of minimizing subject risk by sequentially studying ascending doses. As time-effects are expected to be small relative to the differences between the doses in the broad range investigated, unbiased comparisons between treatments can still be expected.

It is standard in trials involving healthy volunteers to include a placebo group as control for the evaluation of safety and tolerability. Each dose group consists of 8 subjects with 6 on active treatment, and 2 on placebo. The placebo control group includes all subjects of all dose groups treated with placebo. 6 subjects per active treatment group are in general considered as sufficient for the exploratory evaluation of pharmacokinetics.

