4.1.6 Blinding and procedures for unblinding

4.1.6.1 Blinding

The treatments administered will be blinded to subjects only (single-blind). With the rising dose design, single-blind conditions regarding the subjects' treatment (active or placebo) are maintained within each dose group, however the current dose level will be known to subjects and investigators.

The database of this trial will be handled in an open-label fashion, because no bias with regard to data cleaning of safety measures is expected. This is considered acceptable because the potential for bias seems to be low and does not outweigh practical considerations.

The Bioanalyst of the analytical laboratory, the Trial Pharmacokineticist and the Trial Pharmacometrist may receive the randomisation codes prior to official unblinding to perform preliminary PK analyses. He or she will treat the codes confidentially.

In addition, the Drug Metabolism Scientist may receive the randomisation codes prior to official unblinding to perform metabolites in safety testing analysis (MIST). He or she will confirm in writing that the codes will be treated confidentially.

Within the ECG laboratory, the staff involved with interval measurements and assessments will be blinded with respect to the treatment within each dose level and also with regard to the recording date and time as well as time the points of the ECGs. The interval measurements for a given subject will be performed in a random and blinded sequence by a single technician. No more than two different blinded readers will evaluate the ECGs of the study.

Proprietary confidential information © 2017 Boehringer Ingelheim International GmbH or one or more of its affiliated companies

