4.1.6.2 Procedures for emergency unblinding

As this trial will be conducted single-blinded, the treatment information will be known. Therefore, no emergency envelopes will be provided.

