5.2 SAFETY

5.2.1 Endpoints of safety

Primary endpoint to assess safety and tolerability of BI 473494 is the number [N (%)] of subjects with drug-related adverse events.

Further criteria of interest:

- AEs (including clinically relevant findings from the physical examination)
- Safety laboratory tests
- 12-lead ECG
- Vital signs (blood pressure, pulse rate,

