Severe: ≥ 6 episodes in 24 hours (individual episodes separated by at least 5 min) or requiring intravenous fluids, or vomiting that persists despite of anti-emetic treatment

Causal relationship of AEs

Medical judgment should be used to determine the relationship, considering all relevant factors, including pattern of reaction, temporal relationship, de-challenge or re-challenge, confounding factors such as concomitant medication, concomitant diseases and relevant history.

Arguments that may suggest that there is a reasonable possibility of a causal relationship could be:

- The event is consistent with the known pharmacology of the drug
- The event is known to be caused by or attributed to the drug class.
- A plausible time to onset of the event relative to the time of drug exposure.
- Evidence that the event is reproducible when the drug is re-introduced
- No medically sound alternative aetiologies that could explain the event (e.g. pre-existing or concomitant diseases, or co-medications).
- The event is typically drug-related and infrequent in the general population not exposed to drugs (e.g. Stevens-Johnson syndrome).
- An indication of dose-response (i.e. greater effect size if the dose is increased, smaller effect size if dose is diminished).

Arguments that may suggest that there is no reasonable possibility of a causal relationship could be:

- No plausible time to onset of the event relative to the time of drug exposure is evident (e.g. pre-treatment cases, diagnosis of cancer or chronic disease within days / weeks of drug administration; an allergic reaction weeks after discontinuation of the drug concerned)
- Continuation of the event despite the withdrawal of the medication, taking into account the pharmacological properties of the compound (e.g. after 5 half-lives). Of note, this criterion may not be applicable to events whose time course is prolonged despite removing the original trigger.
- Additional arguments amongst those stated before, like alternative explanation (e.g. situations where other drugs or underlying diseases appear to provide a more likely explanation for the observed event than the drug concerned).
- Disappearance of the event even though the trial drug treatment continues or remains unchanged.

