The REP for BI 473494, when measurable drug levels or PD effects are still likely to be present after the last administration, is not known for this first-in-human trial. Therefore, all AEs reported until the end of trial examination (last per protocol contact) will be considered on treatment; please see [Section 7.3.3](#).

AE reporting to sponsor and timelines

The Investigator must report SAEs, AESIs, and non-serious AEs which are relevant for the reported SAE or AESI, on the BI SAE form via fax immediately (within 24 hours) to the Sponsor's unique entry point (country specific contact details will be provided in the ISF). The same timeline applies if follow-up information becomes available. In specific occasions the Investigator could inform the Sponsor upfront via telephone. This does not replace the requirement to complete and fax the BI SAE form.

With receipt of any further information to these events, a follow-up SAE form has to be provided. For follow-up information the same rules and timeline apply as for initial information.

Information required

For each AE, the Investigator should provide the information requested on the appropriate CRF pages and the BI SAE form, if applicable. The Investigator should determine the causal relationship to the trial medication and any possible interactions between the trial medication

The following should also be recorded as an (S)AE in the CRF and BI SAE form (if applicable):

- Worsening of the underlying disease or of other pre-existing conditions

Proprietary confidential information © 2017 Boehringer Ingelheim International GmbH or one or more of its affiliated companies

- Changes in vital signs, ECG, physical examination and laboratory test results, if they are judged clinically relevant by the Investigator.

If such abnormalities already pre-exist prior to trial inclusion they will be considered as baseline conditions and should be collected in the eCRF only.

All (S)AEs, including those persisting after individual subject's end of trial must be followed up until they have resolved, have been assessed as 'chronic' or 'stable', or no further information can be obtained.

Hypoglycaemia

Hypoglycaemic events will be recorded as AEs if symptomatic, or if plasma glucose levels are below 54 mg/dL (in safety laboratory) or blood glucose levels are below 49 mg/dL (in bedside test).

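### Does Protocol 3.2 need rewording because it expects unbiased treatment comparisons while an unblinded investigator judges which adverse events are drug-related?

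*Protocol*

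**What the plan says.** Protocol 3.2 is open about the price of a rising-dose design: "The disadvantage of this trial design is a possible observer bias with regard to the dose-dependent effects as well as time effects". It then notes that time effects should be minor beside the gaps between doses over so wide a range, and concludes that "unbiased comparisons between treatments can still be expected".

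Protocol 5.2.1 sets the endpoint: "Primary endpoint to assess safety and tolerability of BI 473494 is the number [N (%)] of subjects with drug-related adverse events". Under Protocol 5.2.2.1, "Medical judgment should be used to determine the relationship, considering all relevant factors", and Protocol 5.2.2.2 says who does this: "The Investigator should determine the causal relationship to the trial medication". Protocol 4.1.6.1 blinds the subjects only, and Protocol 4.1.6.2 adds: "As this trial will be conducted single-blinded, the treatment information will be known". One group of assessors is shielded: "Within the ECG laboratory, the staff involved with interval measurements and assessments will be blinded with respect to the treatment within each dose level".

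Protocol 7.2 and 7.3.3 make the safety analysis descriptive, with each active dose set against placebo pooled over all dose groups. SAP 4 records that escalation stopped after the 75 µg group and limits all analyses to the first two dose groups.

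**The concern.** Two threats are raised and only one is answered. Observer bias drops out between the sentence that names it and the sentence that concludes. The argument that is made compares time effects with differences between doses, whereas the primary objective compares active doses with placebo. The unanswered threat falls on the primary endpoint, where a subject's status depends on a judgement by someone who knows the treatment.

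A reader who took the conclusion at face value might treat a difference from placebo in drug-related events, or the absence of one, as free of observer bias. In a descriptive trial that contrast is the main result, so an overstated property could matter. SAP 3 also sends readers to the protocol for design background, and neither SAP 7.4 nor SAP 7.8.1 adds a caution.

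**Working it through.** No figure in the plan is disputed. The planned counts reproduce (Protocol 7.6): 11 dose groups × 8 = 88 subjects, of whom 11 × 6 = 66 active and 11 × 2 = 22 placebo.

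**1. Is the gap real?** The passages line up as follows.

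| Threat | Where raised | Where answered |
|---|---|---|
| Time effects | Protocol 3.2 | Protocol 3.2, by comparison with dose differences |
| Observer bias | Protocol 3.2 | Not answered for relatedness |

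The phrase in 3.2 can be read as two disadvantages, or as observer bias acting on both kinds of effect. Observer bias goes unanswered on either reading. Two other passages might have filled the gap and do not. The remark in Protocol 4.1.6.1 that the potential for bias is low concerns the open-label database and data cleaning. The blinding of the ECG readers protects interval measurements, not causality calls. So the gap exists.

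**2. What could it do to the result?** Let r be the proportion of subjects with any adverse event, equal in both arms. Let a(A) and a(P) be the proportions of those subjects who have an event called drug-related on active and on placebo. Then

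spurious difference = r × [a(A) − a(P)].

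The documents give none of these three quantities. Under assumed values only:

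- r = 30%, attribution 50% and 50%: 15% − 15% = 0 points.
- r = 30%, attribution 60% and 40%: 18% − 12% = +6 points.
- r = 30%, attribution 40% and 60%: 12% − 18% = −6 points.
- r from 20% to 50%, attribution gap from 20 to 60 points either way: from ±(0.20 × 0.20) = ±4 points to ±(0.50 × 0.60) = ±30 points.

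Size and sign come entirely from the assumptions. The calculation shows that bias is possible. It does not estimate it.

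**3. How fine is the comparison in any case?** With the two groups that the SAP analyses, filled as planned, there are 2 × 6 = 12 active and 2 × 2 = 4 placebo subjects. One subject is 1/6 = 16.7 points within an active dose and 1/4 = 25 points on placebo. At this scale the table is read with the individual events, and Protocol 7.3 has all individual data listed.

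**4. What is the reader already told?** Observer bias is conceded immediately before the challenged conclusion. The word single-blind is in the trial title, and Protocol 4.1.6 says who knows what. Nothing needed to interpret the table is hidden.

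**5. What would a rewording alter?** The endpoint, analysis sets, tables and results would all stay the same. SAP 7.8.1 already plans subjects with any adverse event by treatment, system organ class and preferred term, and a separate table for drug-related events. The first avoids the causality call, though events are still elicited and graded by unblinded staff. A caveat would describe a possible bias without reducing it.

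**The case for a change.** The best case for a change is that the closing sentence takes back the disclosure that precedes it, and that two sentences and a table footnote would put this right at almost no cost. The premise has also weakened. The planned range was 8.5 mg / 35 µg = 8500 / 35, about 243-fold; the range analysed is 75 / 35, about 2.14-fold, so it is no longer wide. Placebo is pooled over sequential dose groups, so time effects could touch the active-placebo contrast as well.

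Much of this stands. The sentence claims more than its argument supports, and the appeal to a broad range no longer fits the data. But the sentence is design rationale in a protocol of May 2017, and no analysis step depends on it. Rewriting it once escalation has ended would not change how any subject was assessed or counted. A report author discussing drug-related events will naturally say that relatedness was judged with treatment known, and the design statements already in the protocol supply that.

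Two further arguments do not carry over. The sponsor's termination criterion in Protocol 3.3.4.2 also uses drug-relatedness, but it is not a comparison between treatments, so a sentence about comparisons has no bearing on it. Protocol 4.1.3 sends the allocation list to the site in advance, but that concerns assignment within the randomised third cohort and not observer bias. Numbers there are given in order of arrival and cannot be reassigned, and the point has no effect now that escalation has stopped.

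**Conclusion.** The wording of Protocol 3.2 is loose: it draws a general conclusion from an argument about time effects and leaves unblinded relatedness judgements on the primary endpoint uncovered. No change to the plan follows, because there is nothing to gain. The risk is disclosed one sentence earlier, the single-blind design is an openly stated trade-off in an exploratory first-in-human trial, no test or decision threshold uses the comparison, and the display that avoids the causality call is already planned.

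The size of any bias is undetermined. It is zero under equal attribution and could take either sign otherwise. The conclusion assumes that both adverse event tables in SAP 7.8.1 are produced and read together, and that the contrast with placebo stays descriptive, as Protocol 7.2 requires. The counts of 12 active and 4 placebo subjects assume that both dose groups were filled as planned, since the documents do not state actual enrolment.
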